5.12. Pharmacokinetic Sampling

Blood samples for analysis of CK-2127107, its metabolites, and riluzole will be collected from patients at the nominal time points listed in [Table 3](#).

Table 3: Pharmacokinetic (PK) Samples

Day	Sample Time Points
Day 1	Pre-dose and 1 (\pm 15 min) hour post-dose
Week 2	Pre-dose and 1 (\pm 15 min) hour post-dose
Week 4	Pre-dose
Week 8	Pre-dose
Week 12	Pre-dose and 1 (\pm 15 min) hour post-dose

If an indwelling catheter is used, saline flushes will be used. In some cases, sites may be unable to obtain the 6 hour timepoint at Week 2 or Week 12 for logistical reasons; these cases should be discussed with the medical monitor preferably ahead of time.

After completion of bioanalysis, remaining plasma samples will be retained consistent with the Sponsor's standard operating procedures. These samples will not be used for pharmacogenomic testing.

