8.4.7. Pharmacokinetic Analysis

PK analyses will be conducted using the PKS. All of the PK samples collected, including those obtained at Hour 3 on Day 1 as well as Hour 3 and Hour 6 at Week 2 and Week 12 from patients enrolled prior to Amendment 03, will be used for PK analyses. PK parameters such as t_{max} , C_{max} ,

C_{trough} , AUC_{0-24} , AUC_{∞} , CL/F , V/F , $t_{1/2}$ and R_{AC} will be summarized by dose group using descriptive statistics as appropriate. Nominal sample times will be presented in all statistical and graphical summaries.

The observed plasma concentrations of CK-2127107 and its metabolites (if applicable) and riluzole at planned sampling time points will be summarized and listed. The potential for drug-drug interaction between CK-2127107 given alone and in the presence of riluzole will also be assessed.

The PK parameters with and without co-administration of riluzole will also be summarized. Box-whiskers-plots of AUC and C_{max} at Visit Week 12 with and without co-administration of riluzole will be presented.

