Selected PK parameters (eg, AUC_{12} , C_{max} and C_{trough} at Week 12) between patients who took reldesemtiv alone and those who took reldesemtiv plus edaravone will be compared. The natural log-transformed least square mean difference and the associated 90% CI will be calculated using a linear regression model that includes model terms of dose level, edaravone use status at baseline, and interaction of dose level by edaravone use status. An unstructured covariance matrix will be used for the model. Back-transformation will provide point estimates and 90% CIs for the geometric mean ratio that indicates the magnitude of drug interaction. Summaries of selected PK parameters will be presented graphically by dose level, as appropriate.

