12. CHANGES TO ANALYSES SPECIFIED IN PROTOCOL

Not available.

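### SAP 9.1 omits the riluzole PK interaction analysis specified in Protocol 8.4.7 and compares only by edaravone use, without adjusting for riluzole or recording the change

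*SAP*

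**What the plan says.** Protocol 8.4.7 commits to three riluzole outputs:

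- an interaction assessment: "The potential for drug-drug interaction between CK-2127107 given alone and in the presence of riluzole will also be assessed";
- a summary: "The PK parameters with and without co-administration of riluzole will also be summarized";
- Week 12 box plots of AUC and C_max, which "with and without co-administration of riluzole will be presented".

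Protocol 5.12 provides the assay: "Blood samples for analysis of CK-2127107, its metabolites, and riluzole will be collected". The protocol plans no PK comparison by edaravone use.

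SAP 9.1 calculates riluzole concentrations and parameters and summarizes them by dose level. Its one between-group interaction comparison concerns edaravone: for selected PK parameters, "patients who took reldesemtiv alone and those who took reldesemtiv plus edaravone will be compared". The linear model on the log scale has "model terms of dose level, edaravone use status at baseline, and interaction of dose level by edaravone use status", and the back-transformed geometric mean ratio with its 90% CI is read as the size of the drug interaction. SAP Section 12, on changes to protocol-specified analyses, says "Not available".

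**The concern.** A reader who follows the SAP will produce an edaravone ratio but nothing showing reldesemtiv exposure with and without riluzole, which is the interaction the protocol names. Nothing in the SAP says that this was a decision.

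The edaravone comparison also has a weakness of its own. Patients may take either background drug, both or neither (SAP 7.3 lists all four categories), and neither drug is assigned at random. Without a riluzole term, any riluzole effect on exposure can be credited to edaravone if riluzole use differs between edaravone users and non-users. SAP 9.1 does not define what *alone* means, so the reference group is open to two readings.

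**Working it through.** The documents state no sample size, precision or margin for this comparison, so there is no plan figure to reproduce. The first two steps compare texts; the last three illustrate the possible bias on assumed inputs.

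**1. Commitments against the SAP**

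| Protocol 8.4.7 | SAP 9.1 |
|---|---|
| Interaction assessment, with and without riluzole | Absent; comparison by edaravone use instead |
| PK parameters summarized by riluzole co-administration | Absent; parameters summarized by dose level |
| Week 12 AUC and C_max box plots by riluzole | Absent; plots by dose level only |
| No edaravone PK comparison | Edaravone model added |

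**2. Is the analysis elsewhere in the SAP?** No.

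- SAP 9.2 and the PK/PD code in Section 13 (items 4 and 5) include riluzole use, but they model pharmacodynamic response, not reldesemtiv exposure.
- SAP 6.1, 6.4, 8.1 and 8.2 break down disposition, baseline data, adverse events and drug exposure by riluzole and edaravone status. None reports plasma PK that way.
- Riluzole levels by reldesemtiv dose describe the reverse direction and cannot show reldesemtiv exposure by riluzole use.

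**3. How the edaravone ratio could be biased.** Let p1 and p0 be the shares on riluzole among edaravone users and non-users. Stratified randomization (Protocol 8.1.2) balances dose arms on each drug; it does not make p1 equal p0. If riluzole multiplies exposure by a constant ratio, omitting it gives

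apparent edaravone ratio = true edaravone ratio × (riluzole ratio)^(p1 − p0).

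The documents give none of p1, p0 or the riluzole ratio. The values below are assumptions, with the true edaravone ratio set to 1.

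| Assumed riluzole ratio | p1 − p0 = −0.2 | 0 | +0.2 | +0.4 |
|---|---|---|---|---|
| 0.8 | 1.05 | 1.00 | 0.96 | 0.91 |
| 1.1 | 0.98 | 1.00 | 1.02 | 1.04 |
| 1.25 | 0.96 | 1.00 | 1.05 | 1.09 |
| 1.5 | 0.92 | 1.00 | 1.08 | 1.18 |

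The factor is exactly 1 if riluzole use is balanced across edaravone groups, or if riluzole does not affect exposure.

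**4. Check by simulation.** Assumptions: 300,000 patients, 25% on edaravone, log SD 0.5, riluzole ratio 1.25, p1 = 0.90, p0 = 0.60, true edaravone ratio 1. The formula gives 1.25^0.30 = 1.069. The SAP model, averaged over the three doses, returned 1.071. With a riluzole term added, the edaravone ratio was 1.001 and the riluzole ratio 1.254.

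**5. Would defining *alone* as neither drug help?** Take a riluzole ratio of 1.25 and p1 = 0.80. If the reference is all edaravone non-users with p0 = 0.60, the factor is 1.25^0.20 = 1.046. If it is patients on neither drug, p0 = 0 and the factor is 1.25^0.80 = 1.195. Without adjustment, the restriction can make matters worse.

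**The case against.** Several points on the other side are fair.

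- **Status.** No objective or endpoint in either document names a riluzole interaction. The protocol asks for an assessment, summaries and plots; it promises no model, ratio or interval. This stands: what is lost is a specified PK analysis, not a trial objective.
- **Latitude.** Protocol 8.7 lets the SAP change methods, with documentation in the study report. This also stands: the change is not forbidden. The defect is that it is unacknowledged.
- **Riluzole is still analysed.** True, but only as an analyte by dose level, which does not answer the protocol's question.
- **Sampling.** SAP 9.1 derives AUC12 and C_max only for patients enrolled before Amendment 03, so the promised plots cannot cover everyone. This limits the plots but does not explain the omission: the edaravone comparison names the same parameters, and C_trough is planned for all patients.

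A reader might infer that the edaravone ratio *is* confounded, or that the reference group certainly contains riluzole users. The documents support neither. The overlap of the two drugs and any riluzole effect are not given, and *alone* is undefined, although the model's coding by edaravone use suggests that it means no edaravone.

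A reader might also attach a precision to a riluzole ratio on C_trough. The only variability figures given (Protocol 3.3, CVs of 44.1% and 35.9%) are for predicted C_max from Phase 1 modelling, so no such precision is claimed here.

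**Conclusion.** The omission is established by the text alone: none of the three riluzole outputs in Protocol 8.4.7 appears in the SAP, an edaravone comparison stands in their place, and Section 12 records nothing. This should be corrected, but it is a PK matter and does not touch the primary or secondary efficacy tests.

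Confounding of the edaravone ratio is a possibility, not a finding. It needs both unequal riluzole use by edaravone status and a riluzole effect on reldesemtiv exposure. On the assumed ranges above the distortion runs from 0.91 to 1.18, in either direction, and may be nil. The calculation assumes a riluzole effect that is constant across doses and edaravone groups.

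**What to change.** Before database lock:

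1. Add baseline riluzole use to the SAP 9.1 linear model beside edaravone use, keeping all reldesemtiv-treated PKS patients. Report the geometric mean ratio with 90% CI for each drug, adjusted for the other. The protocol does not require a ratio for riluzole; this applies the SAP's own edaravone method to the question that the protocol asked.
2. State the edaravone contrast as use versus non-use adjusted for riluzole. Drop the undefined *alone* group, and do not restrict the reference to patients on neither drug.
3. Restore the with/without riluzole summaries and plots, using C_trough for all patients and AUC12 and C_max for patients enrolled before Amendment 03, labelled as such.
4. Record the added edaravone comparison in Section 12.

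The cost is one model term and a few outputs, with no new data. The AUC and C_max results will rest on the earlier subset, whose size the documents do not give. If use of the two drugs overlaps heavily, the adjusted intervals will widen. Both ratios remain observational, because use of either drug is not randomized.

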9.2. Pharmacokinetic/Pharmacodynamic Analyses

PD analyses may be performed to explore the PK/PD relationship based on the PKs. PD measures will include, but not limited to, the following assessments:

- Percent predicted SVC
- Muscle strength mega score
- ALSFRS-R
- ALSAQ-5

The change from baseline analyses will use the same model as for analysis of the primary efficacy endpoint, except that the model term ‘Treatment’ will be replaced by ‘Concentration’ (a continuous variable, plasma concentration of reldesemtiv) or ‘Concentration Bin’ (a categorical variable that includes placebo group and approximately equal number of patients in each classified reldesemtiv concentration bin).

10. HEALTH ECONOMIC OUTCOMES ANALYSIS

The prescription of non-invasive ventilation, gastrostomy tube, Manual wheelchair, power wheelchair, or augmentative and alternative communication will be analyzed. For patients who were prescribed and agree to receive the items above, the event will be set as 1, and the date of prescription will be used as the event date. For patients who were not prescribed or agreed to receive the items above, the event will be set as 0, and data will be censored at their last date of study visit. Time to event will be summarized by each dose group for patients with an event, and the differences of time to event between each reldesemtiv dose group vs. placebo will be tested using the log-rank test. In addition, the hazard ratios of each reldesemtiv dose group vs. placebo as well as the hazard for the assumed dose response trend (-5, -1, 3, 3) will be calculated using the proportional hazard Cox regression model.

11. COMPUTER METHODS

Statistical analyses will be performed using Version 9.4 (or newer) of SAS[®]. SAS and all other SAS Institute Inc. product or service names are registered trademarks or trademarks of SAS Institute Inc. in USA and other countries.

12. CHANGES TO ANALYSES SPECIFIED IN PROTOCOL

Not available.

13. STATISTICAL CODES

The following code will be used as the prototype of the codes that will be used for the final analysis of the study. The final version of the statistical codes to be used will be determined prior to the database lock and will be documented in the specification document for the statistical report of the study.

1. The SAS code to produce the estimates of the dose response relationship among treatment groups:

For continuous variables:

```
PROC MIXED data = work METHOD = REML;
class <Patient> <Pooled Site> <Visit> <Treatment> <Riluzole Use> <Edaravone Use>;
model <Continuous Variable> = <Pooled Site> <Visit> <Treatment> <Baseline Value> <Riluzole Use> <Edaravone Use>
    <Interaction between Visit and Treatment> <Interaction between Visit and Baseline Value> / ddfm = kenwardroger; repeated
<Visit> / subject = <Patient> type = un;
lsmeans <Visit>*<Treatment> / pdiff cl;
lsmestimate <Visit>*<Treatment> `300mg and 450mg - placebo at week 2' [-1,1 1] [0,1 2] [0.5,1 3] [0.5,1 4] / cl;
lsmestimate <Visit>*<Treatment> `300mg and 450mg - placebo at week 4' [-1,2 1] [0,2 2] [0.5,2 3] [0.5,2 4] / cl;
lsmestimate <Visit>*<Treatment> `300mg and 450mg - placebo at week 8' [-1,3 1] [0,3 2] [0.5,3 3] [0.5,3 4] / cl;
lsmestimate <Visit>*<Treatment> `300mg and 450mg - placebo at week 12' [-1,4 1] [0,4 2] [0.5,4 3] [0.5,4 4] / cl;
lsmestimate <Visit>*<Treatment> `Contrast at week 2' [-0.83333,1 1] [-0.16666,1 2] [0.5,1 3] [0.5,1 4] / cl;
lsmestimate <Visit>*<Treatment> `Contrast at week 4' [-0.83333,2 1] [-0.16666,2 2] [0.5,2 3] [0.5,2 4] / cl;
lsmestimate <Visit>*<Treatment> `Contrast at week 8' [-0.83333,3 1] [-0.16666,3 2] [0.5,3 3] [0.5,3 4] / cl;
lsmestimate <Visit>*<Treatment> `Contrast at week 12' [-0.83333,4 1] [-0.16666,4 2] [0.5,4 3] [0.5,4 4] / cl;
ods output LSMeans = lsm Diffs = diff LSMEstimates = lsmest;
run;
```

Note: Include outcome measurements collected at Weeks 2, 4, 8 and 12. For the endpoints of percent change from baseline (e.g., muscle strength mega score), the term "baseline value" and the interaction term <Interaction between Visit and Baseline Value> will be excluded from the model.

2. The SAS code to produce estimates of slope:

```
PROC MIXED data = work METHOD = REML;
class <Patient> <Pooled Site> <Treatment> <Riluzole Use> <Edaravone Use>;
model <Continuous Variable> = <Pooled Site> <Days from First Dose> <Treatment> <Baseline Value> <Riluzole Use>
    <Edaravone Use> <Interaction between Treatment and Day> <Interaction between Treatment and Baseline Value> / ddfm =
kenwardroger noint;
random <Day> / subject = <Patient>;

estimate 'slope for placebo' <Day> 1 <Interaction between Day and Treatment> 1 0 0 0 / cl;
estimate 'slope for 150mg' <Day> 1 <Interaction between Day and Treatment> 0 1 0 0 / cl;
estimate 'slope for 300mg' <Day> 1 <Interaction between Day and Treatment> 0 0 1 0 / cl;
estimate 'slope for 450mg' <Day> 1 <Interaction between Day and Treatment> 0 0 0 1 / cl;
estimate 'slope for 300 & 450mg' <Day> 1 <Interaction between Day and Treatment> 0 0 0.5 0.5 / cl;
estimate 'slope 150mg - placebo' <Interaction between Day and Treatment> -1 1 0 0 / cl;
estimate 'slope for 300mg - placebo' <Interaction between Day and Treatment> -1 0 1 0 / cl;
estimate 'slope for 450mg - placebo' <Interaction between Day and Treatment> -1 0 0 1 / cl;
estimate 'slope for 300mg & 450mg combined - placebo' <Interaction between Day and Treatment> -1 0 0.5 0.5 / cl;
estimate 'slope for contrast' <Interaction between Day and Treatment> -0.83333 -0.1666 0.5 0.5 / cl;

ods output Estimates = est SolutionF = sf;
run;
```

- Note: The variable 'Day' = days from the 1st dose. Include outcome measurements collected at baseline, Weeks 2, 4, 8, 12. For the endpoints of slope of percent change from baseline (e.g., slope of muscle strength mega score), the terms "baseline value" and "interaction between Treatment and Baseline" will be excluded from the model, and the interaction terms "Treatment-by-Riluzole use status" and "Treatment-by-Edaravone use status" will be added to the model.

3. The SAS code to produce time to event analysis results among treatment groups:

```
PROC LIFETEST data = work;
time <Event Variable><Censor Variable(1)>;
strata <Treatment>;
ods output CensoredSummary=sum Quartiles=quart HomTests=test;
run;

PROC PHREG data = work;
class <Pooled Site> <Riluzole Use> <Edaravone Use>;
model <Event Variable> <Censor Variable(1)> = <Treatment> <Baseline Value>;
strata <Pooled Site> <Riluzole Use> <Edaravone Use>;
Contrast '150 mg - placebo' <Treatment> -1 1 0 0 / Estimate=exp;
```

```
Contrast `300 mg - placebo' <Treatment> -1 0 1 0 / Estimate=exp;  
Contrast `450 mg - placebo' <Treatment> -1 0 0 1 / Estimate=exp;  
Contrast `300 and 450 mg - placebo' <Treatment> -1 0 0.5 0.5 / Estimate=exp;  
Contrast `Contrast' <Treatment> -0.83333 -0.1666 0.5 0.5 / Estimate=exp;  
ods output ContrastEstimate=est;  
run;
```

Note: Include outcome measurements collected at baseline, Weeks 2, 4, 8, 12. For the endpoints of slope of percent change from baseline (e.g., slope of muscle strength mega score), the term "baseline value" will be excluded from the model.

4. The SAS code to produce estimates of slope for concentration effect PK/PD analyses:

Slope 1:

```
PROC MIXED data = work METHOD = REML;  
class <Patient> <Pooled Site> <Riluzole Use> <Edaravone Use>;  
model <Efficacy Continuous Variable> = <Day> <Pooled Site> <Concentration> <Baseline Value> <Riluzole Use> <Edaravone Use> /  
    ddfm=kenwardroger s;  
random <Day> / subject = <Patient>;  
ods output SolutionF = sf;  
run;
```

Slope 2:

```
PROC MIXED data = work METHOD = REML;  
class <Patient> <Pooled Site> <Visit> <Riluzole Use> <Edaravone Use>;  
model <Continuous Variable> = <Pooled Site> <Visit> <Concentration> <Baseline Value> <Riluzole Use> <Edaravone Use>  
    <Interaction between Concentration and Visit> <Interaction between Concentration and Baseline Value>/ ddfm=kenwardroger  
s;  
estimate `slope of concentration at Week 2' <Concentration> 1 <Interaction between Visit and Concentration> 1 0 0 0/ cl;  
estimate `slope of concentration at Week 4' <Concentration> 1 <Interaction between Visit and Concentration> 0 1 0 0/ cl;  
estimate `slope of concentration at Week 8' <Concentration> 1 <Interaction between Visit and Concentration> 0 0 1 0/ cl;  
estimate `slope of concentration at Week 12' <Concentration> 1 <Interaction between Visit and Concentration> 0 0 0 1/ cl;  
  
ods output SolutionF = sf estimates = est;  
run;
```

Note: The variable 'Day' = days from the 1st dose. Include outcome measurements collected at Weeks 2, 4, 8, 12. For the endpoints of percent change from baseline (e.g., muscle strength mega score), the terms "baseline value" and "Interaction between Visit and Baseline Value" will be excluded from the model.

5. The SAS code to produce the estimates of concentration bin effect PK/PD analyses:

For continuous PD parameters:

```
PROC MIXED data = work METHOD = REML;
class <Patient> <Pooled Site> <Visit> <Riluzole Use> <Edaravone Use> <Concentration Bin>;
model <Continuous Variable> = <Pooled Site> <Visit> <Concentration Bin> <Baseline Value> <Riluzole Use> <Edaravone Use>
    <Interaction between Visit and Concentration Bin> <Interaction between Concentration Bin and Baseline Value> /
    ddfm=kenwardroger s;
repeated <Visit> / subject = <Patient> type = un;
lsmeans <Visit>*<Concentration Bin> / pdiff cl;
ods output lsmeans = lsm diffs = diff;
run;
```

Note: For the endpoints of percent change from baseline (e.g., muscle strength mega score), the terms "baseline value" and "Interaction between Visit and Baseline Value" will be excluded from the model.

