8.1.2. Sample Size and Randomization

Approximately 445 patients will be randomized to receive either one of the three CK-2127107 doses (300 mg/day, 600 mg/day and 900 mg/day TDD) or matching placebo tablets in a ratio of 1:1:1:1. Randomization will be stratified by riluzole use/non-use and edaravone use/non-use. The dropout rate at Visit Week 12 is estimated to be 10%, thus approximately 400 patients are expected to complete 12 weeks of double-blind treatment. The effect of CK-2127107 on the change from baseline to Week 12 in percent predicted SVC will be analyzed using a mixed model for repeated measures (MMRM) with the contrast (-5, -1, 3, 3) to reflect the assumed relationship for the placebo, 300 mg/day, 600 mg/day and 900 mg/day dose groups. The analysis is estimated to provide 90% power to detect 2.75, 5.5 and 5.5 percentage points advantage over placebo for the 300 mg/day, 600 mg/day and 900 mg/day CK-2127107 dose groups, respectively, in change from baseline of percent predicted SVC, at the end of the double-blind treatment (Visit Week 12). This calculation is based on a two-sided test with alpha set at 0.05 and a common standard deviation of 14 percentage points.

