5.4.3. Pharmacokinetics Analysis Set

The Pharmacokinetics Analysis Set (PKS) will consist of all randomized patients who have at least one evaluable plasma concentration of reldesemtiv, provided they have no major protocol violations that could affect the PK results of reldesemtiv.

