7. EFFICACY

Inferential statistical tests will be two-sided and will be performed at alpha levels of 0.05 to declare the significance of effects.

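### The printed PK/PD Slope 2 code contradicts SAP 9.2: it has no within-patient covariance and takes the concentration slope at baseline 0 (minor)

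*SAP*

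**What the plan says.** **Text model.** SAP 9.2 says: "The change from baseline analyses will use the same model as for analysis of the primary efficacy endpoint". The Treatment term is swapped for plasma concentration, either continuous or in bins. The primary model in SAP 7.5.1 has visit, baseline and baseline-by-visit terms and an unstructured covariance for the within-patient errors.

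**Printed code.** SAP 13, item 4, Slope 2 is a PROC MIXED block on the Week 2, 4, 8 and 12 data.
- Its interactions are concentration-by-visit and concentration-by-baseline. There is no visit-by-baseline term.
- It contains neither REPEATED nor RANDOM.
- Its four ESTIMATE lines, the last labelled "slope of concentration at Week 12", weight concentration and concentration-by-visit only.

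**Analysis set.** SAP Table 2 assigns PK/PD analyses to the PKS, defined in SAP 5.4.3 as "all randomized patients who have at least one evaluable plasma concentration of reldesemtiv" without major violations affecting PK. SAP 9.2 describes Concentration Bin as "a categorical variable that includes placebo group".

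**Status.** SAP 13 calls the code a prototype, to be finalized before database lock. SAP 9.2 makes the PK/PD analyses optional.

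**The concern.** The code and the text specify different models, and the printed one gives wrong standard errors. Four correlated rows per patient are treated as four independent observations with one common variance. The reported slope is also an extrapolation: for percent predicted SVC it refers to a patient with a baseline of 0, and Protocol 4.1 admits nobody below 60% at screening.

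Exposure–response is a stated PK/PD objective (Protocol 2.4, SAP 2.1.4). SAP 8.4 also refers to the Section 9.2 method for the analysis of eGFR change against trough concentration. A p-value from Slope 2 as printed would overstate the evidence for a concentration effect.

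The placebo question is separate. If placebo patients are left out, the zero-concentration end of the range is lost.

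**Working it through.** **1. The plan's own figure.** No operating figure is given for Slope 2. The only design figure is for the primary contrast: "The analysis is estimated to provide 90% power to detect 2.75, 5.5 and 5.5 percentage points advantage over placebo", based on "a two-sided test with alpha set at 0.05 and a common standard deviation of 14 percentage points".
- Contrast value: −1×2.75 + 3×5.5 + 3×5.5 = 30.25.
- Sum of squared coefficients: 25 + 1 + 9 + 9 = 44.
- With 100 completers per arm, SE = 14×√(44/100) = 9.29.
- Power = Φ(30.25/9.29 − 1.96) = Φ(1.30) = 0.90, and 400/0.9 = 444.4, so 445 randomized.

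This reproduces, and nothing below affects it.

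**2. Code against code.** In SAP 13, items 1 and 5 have REPEATED with type=un, and item 2 and Slope 1 have RANDOM. Slope 2 is the only PROC MIXED block with neither. The notes under items 4 and 5 tell the programmer to drop a visit-by-baseline term for percent-change endpoints, but neither Slope 2 nor item 5 contains one. That points to a slip in the printed interaction.

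**3. What the ESTIMATE lines compute.** The Week 12 slope at baseline b is (concentration) + (concentration-by-visit, Week 12) + b × (concentration-by-baseline). With no coefficient on the last term, b = 0.

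**4. Simulated type I error.** A true null was used, with 1,000 trials per scenario (Monte Carlo SE about 0.7 percentage points).
- From the documents: two-sided 0.05, Week 12 SD 14, SVC floor 60, and Cmax 1789 (CV 44.1%) to 5543 (CV 35.9%) ng/mL from Protocol 3.3.
- Assumed: interpolated middle-dose Cmax; baseline SVC mean about 85 and SD 16; visit SDs 14 throughout, 8/10/12/14 or 5/7/10.5/14; equal between-visit correlation; within-patient concentration CV 25%; complete data; placebo in or out.

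Rejection rates for the Week 12 slope, correlation 0.5–0.85:

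| Covariance | Slope at | Type I error |
|---|---|---|
| Independent (as printed) | baseline 0 | 15.7–28.2% |
| Independent | mean baseline, SD 14 throughout | 4.5–6.1% |
| Independent | mean baseline, SD 8 to 14 | 11.2–12.4% |
| Independent | mean baseline, SD 5 to 14 | 15.9–19.4% |
| Unstructured | baseline 0 | 3.8–6.5% |
| Unstructured | mean baseline | 4.1–7.4% |

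As printed, the rate is about 12% at correlation 0.3 and 4.2–6.1% at correlation 0. Separate runs under other assumed inputs, including AR(1) correlation 0.6–0.8, gave 19–26% as printed and about 4–8% for a Week 12 regression matching SAP 9.2.

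**5. Mechanism, by hand.** Take SD 14 throughout, correlation 0.7, placebo included. As printed, the reported SE is 0.865 at baseline 0 and 0.286 at mean baseline.
- The variance due to concentration-by-baseline is about 0.865² − 0.286² = 0.748 − 0.082 = 0.666.
- That coefficient is shared by all four visits. If concentration were constant within a patient, its true variance would be larger by 1 + 3×0.7 = 3.1.
- True SE ≈ √(0.082 + 3.1×0.666) = √2.147 = 1.47. The simulated value is 1.41, a little lower because concentration varies within patients.
- Expected rejection: 2Φ(−1.96×0.865/1.41) = 2Φ(−1.20) = 0.23. The simulated rate is 0.222.

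**6. Precision.** With unstructured covariance, the SE at baseline 0 is 2.1 times (0.380/0.180) to 4.8 times (0.870/0.180) that at mean baseline. Excluding placebo raises the SE at mean baseline by about 16–32% (for example 0.331 against 0.263) and leaves type I error unchanged.

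**The case against.** The strongest reply is that the governing text is right. SAP 9.2 leads to the correct covariance and interaction, the code is only a prototype, and a programmer following the text would not produce these error rates. That stands as a limit on the consequence: the 16–28% applies only if the printed block is run. It does not remove the contradiction, since SAP 5.3 treats a change of analysis method as grounds for a SAP revision.

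It is also fair that the analysis is exploratory, outside the closed test of SAP 7.4, and that Protocol 3.3 says the study's information as a whole will guide later doses, not this model.

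Stronger readings that a reader might infer are not supported:
- *Each feature invalidates the p-values.* Baseline 0 with a correct covariance is a valid, imprecise test of an uninformative quantity. Leaving out placebo also keeps the type I error. Even independence alone is harmless at mean baseline when the visit SDs are equal.
- *The plan removes placebo from PK/PD.* The PKS wording does so literally, but Section 9.2 includes placebo in the bins and Protocol 5.12 does not limit PK sampling by arm. This is an inconsistency, not a rule.
- *Item 5 shares the fault.* It has REPEATED type=un, and LSMEANS evaluates at mean baseline.
- *A specific loss of power.* The answer depends on a concentration distribution in ALS patients that the documents do not give, and slopes at baseline 0 and at observed baselines are different quantities.

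**Conclusion.** The point holds, as a minor one. Slope 2 as printed contradicts SAP 9.2 in its covariance and its baseline interaction. The two departures together make its Week 12 test anti-conservative: roughly 16–28% type I error at nominal 5% for between-visit correlation of about 0.5–0.85, against about 4–8% for the Section 9.2 model. The size depends on the assumed baseline, visit-SD, correlation and concentration inputs. The direction was the same in every scenario with correlated visits.

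Baseline 0 is outside the data for SVC. For ALSFRS-R it is the worst possible score and for ALSAQ-5 the best, so there it is at an extreme of the scale. For the mega score, the note removes the baseline terms, so the issue arises only if concentration-by-baseline is left in.

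The placebo wording is a separate inconsistency that affects precision only. The primary and secondary analyses and the 90% power are untouched.

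**What to change.** - **Slope 2 (SAP 13, item 4):** add `repeated <Visit> / subject=<Patient> type=un`, and replace concentration-by-baseline with visit-by-baseline, as SAP 9.2 implies. The ESTIMATE lines can then stay as they are.
- **Item 5:** make the same change of interaction, for consistency with Section 9.2 only.
- **Placebo (SAP 5.4.3, Table 2 and 9.2):** state that FAS placebo patients enter the bin analysis, and say whether they enter the continuous-concentration model at concentration 0 or that model is confined to active patients.

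The cost is one line of code, one model term in two blocks and a sentence or two of text, before database lock. No new data, visits or patients are needed.
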